Differences in sensorimotor gating also distinguish certain groups of normal subjects. For example, lower levels of PPI are found in clinically normal individuals who carry the Val/Val vs. Met/Met alleles for the Val158Met polymorphism of the gene for catechol-O-methyltransferase. In other cases, differences in PPI drug sensitivity distinguish certain groups of normal subjects. For example, amphetamine differentially changes PPI among individuals characterized as having low vs. high novelty seeking personalities. For these reasons, some of our studies interrogate specific genetic and personality characteristics of our test subjects: genotyping is conducted using blood samples, and specific questionnaires are used to evaluate personality and behavioral characteristics of the study populations.

Differences in sensorimotor inhibition will be detected by some, but not other laboratory-based measures, reflecting differences in the particular psychophysical demands of the measure. To add to our

understanding of patterns of sensorimotor inhibition across normal and patient populations, and of changes in sensorimotor inhibition in response to specific manipulations of brain circuitry thought to regulate one form of sensorimotor inhibition (PPI), we also assess Latent Inhibition, Negative Priming, Mismatch Negativity and Gamma Band Synchronization in some of our study groups.

Importantly, measures of sensorimotor gating are associated with higher brain functions, including neurocognitive processes. Thus, in some cases, our subjects complete measures of neurocognition, designed specifically to assess drug effects on processes such as working memory. In this way, we can test the hypothesis that drug-induced increases in sensorimotor gating can contribute to neurocognitive improvements in patients populations.

Our current studies are designed to achieve 3 Specific Aims (see Figure 1):

1. To assess the effects of the indirect dopamine agonist, d-amphetamine, on PPI and neurocognition in healthy subjects, and the moderating roles of personality and genotype in these effects. 120 healthy subjects will complete a within-subject study of placebo vs. 20 mg amphetamine (p.o.) on two separate days, completing measures of sensorimotor gating and neurocognition on each test day. All subjects will be characterized in terms of specific genetic and personality characteristics.

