More recent studies have clarified that the sensitivity of PPI to drug effects in normal humans is moderated by several factors, including the presence of specific genes, and personality dimensions associated with those genes. For example, several groups have reported that PPI and its sensitivity to drug challenge differs significantly between normal men who carry different alleles for the COMT Val158Met polymorphism. In these studies, the Val/Val allele is associated with high COMT activity, rapid DA catabolism, high novelty seeking scores, low basal PPI and PPI-enhancing effects of the COMT inhibitor, tolcapone. In contrast, the Met/Met allele is associated with low COMT activity, low DA catabolism, low novelty seeking scores, high basal PPI, and PPI-reducing effects of tolcapone. We previously reported that rats expressing high levels of COMT within the ventral striatum exhibit PPIenhancing effects in response to DA agonists, like amphetamine, while rats expressing low levels of COMT in this region exhibit PPI-reducing effects in response to amphetamine. More recently, we confirmed that normal women with high novelty seeking scores (who as a group predominantly express the Val/Val high activity COMT allele) respond to amphetamine with elevations of PPI, while those with low novelty seeking (associated with the Met/Met low activity COMT allele) respond to amphetamine with reduced PPI. We also detected PPI-enhancing effects of the NMDA antagonist and weak DA agonist, memantine, among men exhibiting low baseline PPI and/or high novelty seeking, both of which are associated with the Val/Val COMT genotype. Thus, across species, genetically determined levels of COMT activity appear to moderate the impact of specific drugs on sensorimotor gating. These findings suggest a biological explanation for a genetically based "vulnerability" to the gating-disrupted effects of increased dopamine activity and/or reduced NMDA activity, thought to be core features of brain disorders such as schizophrenia and Tourette Syndrome. We now plan to extend this work to further clarify the role of COMT polymorphisms and other genetic substrates on the sensitivity of PPI to drug effects in humans.

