Lastly, based on the impact of basal PPI level and personality measures in controls, we hypothesize that a critical moderating factor underlying PPI memantine sensitivity is COMT Val158Met genotype; specifically, we predict that "Val/Val" individuals will be most sensitive to memantine-enhanced PPI. This will be tested in two ways: first, by ANOVA as above, with COMT status as a between-subject factor, and memantine dose and prepulse interval as within-subject factors. Significant genotype x dose or genotype x dose x int interactions, with appropriate post-hoc comparisons, would confirm the hypothesis. Estimating d=1.53, based on the mean "d" of two "COMT phenotypes" in controls - low basal PPI (d=1.80) and high "novelty seeking" personality (d=1.27) - the proposed 11 Val/Val and 7 Met/Met patients/dose group would yield power of 0.90 to detect genotype-sensitive memantine effects. It is possible that various factors (including a skewed distribution of allele frequencies, or substantial genotype effects on basal PPI levels) might preclude detection of a significant 2- or 3-way interaction. A secondary (albeit weaker) test of the hypothesis will utilize separate ANOVAs in Val/Val vs. Met/Met subgroups, with predicted PPI-enhancing effects of memantine in the Val/Val but not Met/Met subgroups. Previous reports also predict a significant main effect of genotype, with PPI levels following the Met/Met>Val/Met>Val/Val gradient. Logistic regressions might be used, with genotype coded to reflect "dose" of the Met allele (Val/Val=0, Val/Met=1, and Met/Met=2), to assess the distribution of the neurophysiological and neurocognitive measures. All analyses will be conducted independently for each dose group. If comparable effects are evident with 10 and 20 mg doses, dose groups may be pooled to increase power for exploratory analyses (e.g. to detect genotype x drug effects).

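### The predicted COMT gradient in PPI is tested on an average of placebo and memantine days, and separately in each dose group, so the plan's own Val/Val drug effect weakens it and may cancel or reverse it

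*Protocol*

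**What the plan says.** The COMT analysis is set out in the protocol, section 9, item j, under the power considerations. It is a mixed ANOVA "with COMT status as a between-subject factor, and memantine dose and prepulse interval as within-subject factors". Within one dose group the drug factor has two levels, placebo and active.

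The main hypothesis is a genotype x drug interaction, and the plan states that "the proposed 11 Val/Val and 7 Met/Met patients/dose group would yield power of 0.90 to detect genotype-sensitive memantine effects". Separate ANOVAs by genotype are the back-up, "with predicted PPI-enhancing effects of memantine in the Val/Val but not Met/Met subgroups". The plan then adds a second prediction: "Previous reports also predict a significant main effect of genotype, with PPI levels following the Met/Met>Val/Met>Val/Val gradient". No effect size or power is given for it.

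The same paragraph says "All analyses will be conducted independently for each dose group". Pooling is allowed only if the two doses behave alike, and then for exploratory work.

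The gradient comes from findings on PPI without memantine. Section 6 says "lower levels of PPI are found in clinically normal individuals who carry the Val/Val vs. Met/Met alleles", and section 7 (Background) says "the Val/Val allele is associated with high COMT activity, rapid DA catabolism, high novelty seeking scores, low basal PPI". No analysis of genotype on placebo-day or screening PPI is specified. A regression on Met-allele count is mentioned as a possibility, without saying which day's data it would use. The SAP contains no genotype analysis.

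**The concern.** The two genotype predictions pull against each other in this term. Val/Val patients are expected to start lowest and to be the ones memantine raises, so the Met/Met minus Val/Val gap should narrow on the memantine day. Averaging the two days mixes the gap the prediction is about with one the drug is expected to have closed in part. The larger the Val/Val response, the weaker the main effect becomes as a test of the gradient. The plan notes that genotype effects on basal PPI might hide the interaction, but not that the interaction shrinks the main effect.

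Splitting by dose adds a separate loss. Every patient has a placebo day, and PPI on that day does not depend on which active dose the patient was assigned. The split leaves 11 Val/Val against 7 Met/Met where 22 against 14 are available.

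At stake is a secondary biological finding: a real gradient could be reported as absent or, if the drug-free gap is small, as pointing the wrong way.

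**Working it through.** **Inputs from the protocol (section 9, item j).** d = 1.53 for the genotype-sensitive effect, the mean of 1.80 and 1.27 in controls; 11 Val/Val and 7 Met/Met per dose group of 30, which leaves 12 Val/Met; alpha 0.05, taken as two-sided.

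**Assumptions, not in the documents.** Drug-free gap g (Met/Met minus Val/Val) of 0.5 to 2.0 single-day SDs; between-day correlation r of 0.5 to 0.8; d scaled either by the single-day SD or by the SD of the change score.

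**The plan's own figure.** For 11 against 7 at d = 1.53, the normal approximation gives power 0.886 and a two-sided t-test 0.844, against the stated 0.90. The stated figure is reproduced to within 2 points by the normal approximation. No power is stated for the genotype main effect.

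**Averaged gap.** Let D be the Val/Val drug effect in single-day SDs, with no effect in Met/Met.
- Placebo-day gap: g. Memantine-day gap: g - D.
- Mean of the two days: g - D/2.
- Only the difference between the two genotypes' drug effects matters, so an equal drug effect in both would not change this.

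**Size of D/2.**
- Single-day scaling: 1.53/2 = 0.765.
- Change-score scaling, D = 1.53 x sqrt(2(1 - r)): r = 0.5 gives 0.765; r = 0.7 gives 1.185/2 = 0.593; r = 0.8 gives 0.968/2 = 0.484.

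**Power.** The two-day mean has SD sqrt((1 + r)/2), which is 0.866, 0.922 and 0.949 at r = 0.5, 0.7 and 0.8. Power is from the noncentral t for Met/Met against Val/Val, two-sided 0.05, counting only rejections in the predicted direction. Ranges cover both scalings and all three r.

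| g | Averaged gap, D/2 = 0.765 | Averaged gap, D/2 = 0.484 | As planned, 11 vs 7 | Placebo day, 11 vs 7 | Placebo day, 22 vs 14 |
|---|---|---|---|---|---|
| 0.5 | -0.265 | 0.016 | 0.01-0.03 | 0.16 | 0.30 |
| 0.8 | 0.035 | 0.316 | 0.03-0.09 | 0.34 | 0.62 |
| 1.0 | 0.235 | 0.516 | 0.07-0.18 | 0.49 | 0.81 |
| 1.5 | 0.735 | 1.016 | 0.33-0.55 | 0.83 | 0.99 |
| 2.0 | 1.235 | 1.516 | 0.72-0.87 | 0.97 | 1.00 |

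**Separating the two changes at g = 1.0.** Using the placebo day alone moves power from 0.07-0.18 to 0.49; pooling then moves it to 0.81. Pooling while still averaging the days gives only 0.10 to 0.34.

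**Three genotypes.** With Val/Met placed midway (an assumption), an omnibus F-test simulation at g = 1.0, r = 0.5 and D = 1.53 gives 0.07 for the averaged main effect (n=30), 0.41 on the placebo day (n=30) and 0.74 on the placebo day (n=60). A linear trend on drug-free PPI with n=60 gives about 0.82.

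**The case against.** **The COMT hypothesis does not rest on this term.** This stands. A reader might infer that a strong Val/Val response would lead the study to contradict its own COMT model. The documents do not support that. The hypothesis is confirmed by the interaction, with genotype-specific ANOVAs as back-up, and a drug effect large enough to hide the gradient would make the interaction easier to find. A significant interaction also directs attention to simple effects rather than to the marginal mean. However, the plan names no placebo-day genotype comparison, and one made within a dose group would still have only 11 against 7.

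**Cancellation is not shown.** This also stands. A reader might infer that the drug effect cancels the gradient outright. That happens only if the drug-free gap is near 0.5 to 0.8 SD. A smaller gap would be reversed, and at 1.5 to 2.0 SD some 49 to 76% of it remains. The documents give no value for the gap.

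**The drug effect is itself uncertain.** The 1.53 averages two phenotype effects in controls. It was not measured by genotype, in patients or at 10 mg. A smaller D means a smaller loss. Under change-score scaling a correlation below 0.5 means a larger one: at r = 0, D/2 = 1.53 x sqrt(2)/2 = 1.08.

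**Screening PPI may be a selected variable.** Section 9, item e allows subjects to be called back according to genotype balance or high and low PPI quartiles. If that was applied to patients, a genotype trend on screening PPI could be distorted. This is why placebo-day PPI should come first.

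**Conclusion.** The concern holds as a mismatch between the gradient and the term used to test it. That the main effect loses half of the Val/Val drug effect follows from the model and the plan's own prediction. The size, about 0.5 to 0.8 SD, assumes that d = 1.53 carries over to patients and to both doses, and that r is 0.5 to 0.8. The gradient is therefore weakened and may be cancelled or reversed; which of these applies depends on a drug-free gap that the documents do not give. The dose split is a second loss, and the conditional, exploratory pooling does not repair it. At every gap in the table, pooled placebo-day PPI has more power than the planned test. The gradient is a secondary prediction with no power claim, and the genotype x drug hypothesis and its test are untouched.

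**What to change.** Add one sentence to the genotype analysis, and carry it into the SAP: the Met/Met to Val/Val gradient is tested on placebo-day PPI, in both dose groups together (n=60), as a linear trend on Met-allele count (0, 1, 2). Use screening PPI as a supporting check only if patients were not selected on it. Keep the memantine-day data for the genotype x drug term, which stays as planned.

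This uses data already to be collected and needs no extra visits or patients. The SAP is written in the past tense, so if the genotype data have already been analysed, the placebo-day trend should be labelled as specified afterwards.

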2. To assess the effects of the NMDA antagonist, memantine, on PPI and neurocognition in healthy subjects, and the moderating roles of personality and genotype in these effects. 30 healthy subjects will complete a within-subject study of placebo vs. 20 mg memantine (p.o.) on two separate days, completing measures of sensorimotor gating and neurocognition on each test day. All subjects will be characterized in terms of specific genetic and personality characteristics.

3. To assess the effects of the NMDA antagonist, memantine, on PPI and neurocognition in schizophrenia patients, and the moderating roles of genotype in these effects. 60 well-characterized and clinically stable individuals with schizophrenia will complete a within-subject study of placebo vs. 10 mg memantine (p.o.) (n=30) or placebo vs. 20 mg memantine (n=30) on two separate days, completing measures of sensorimotor gating and neurocognition on each test day. All subjects will be characterized in terms of specific genetic characteristics.

BACKGROUND AND SIGNIFICANCE 7.

The startle reflex is a constellation of responses to sudden, relatively intense stimuli that is usually classified as a defensive response. One major advantage of startle response paradigms is that the same phenomena can be studied across species. In humans, the blink reflex component of the startle response is measured using electromyography of the orbicularis oculi muscle. Despite its simplicity, startle demonstrates several forms of plasticity - including habituation and fear-potentiation - that are regulated by forebrain circuitry. Even these more complex processes exhibit striking similarities across species, from rodents to humans. One form of startle plasticity is "prepulse inhibition" (PPI), which is the normal suppression of the startle reflex, which occurs when the intense startling stimulus is preceded by a weak prestimulus.

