As described in our past progress reports, we continue to actively test subjects using our proposed measures. They include bilateral measures of eyeblink acoustic startle, prepulse inhibition and habituation of acoustic startle, visuospatial priming and latent inhibition. Additional variations of these measures are developed on a regular basis to enhance their sensitivity.

After completing a series of studies using the non-DA stimulant caffeine, we undertook a systematic series of studies to examine the effects of DA agonists on startle and related measures in normal humans. We assessed the time course of action of several DA agonists - pergolide (0.025 and 0.1 mg), amphetamine (20 mg), amantadine (200 mg) and bromocriptine (1.25 and 2.5 mg) - on startle measures,

autonomic changes, and self-ratings of somatic and physiological symptoms. We then completed detailed, within-subject studies of the effects of amphetamine, amantadine, bromocriptine and pramipexole on PPI and related measures. Findings from these studies were described in published reports, cited in Section 22, and many have already been replicated and extended by other groups.

Most recently, we have begun to assess the broader neurocognitive correlates of drug-induced changes in sensorimotor gating. Our group and others have reported that levels of PPI correlate significantly with global neurocognitive measures, and specifically, with working memory (WM); in schizophrenia patients, we reported that levels of PPI correlate significantly with global levels of functioning. We also reported that the Alzhemier's Disease medication and NMDA antagonist, memantine, significantly increases PPI,

particularly among individuals with phenotypes - low baseline PPI and high novelty seeking - associated with the Val/Val COMT genotype. As a result, we have initiated studies in normal subjects to test the hypothesis that memantine will increase WM, particularly among subjects exhibiting high memantine PPI sensitivity. Our initial findings in a double-blind, within-subject, balanced

Effects of memantine (MEM) vs. placebo (PBO) on WM (%ile score from MCCB, see text). WM was increased by MEM in 7 out of 8 subjects, and unchanged in the 8th. In these subjects (F=10.68, p<0.015), MEM also significantly increased PPI. This ongoing study is conducted with a double- blind, balanced order design.	WM	РВО	* MEM
--	----	-----	----------

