order, placebo-controlled study, are quite promising: memantine (20 mg po) significantly increased WM in normal subjects, despite the fact that most of these subjects are UCSD undergraduate students with high baseline levels of WM (see figure, right). PPI was also significantly increased in these subjects, particularly among the predicted "sensitive" subgroups.

The implications of these preliminary findings are potentially quite significant, as they suggest that MEM might enhance PPI and WM, particularly among subgroups of individuals carrying "biomarkers" that include low baseline PPI, high novelty seeking, and/or the Val/Val COMT genotype. If this same pattern of results is detected in clinical populations, it will suggest a means to prospectively identify patients in whom memantine (or other putative pro-cognitive agents) can enhance specific neurocognitive abilities (e.g. WM) to synergize with therapeutic interventions (e.g. cognitive training) that rely on these abilities. We are currently planning to test this prediction in clinical populations, including patients with schizophrenia, who are enrolled in IRB-approved clinical trials of cognitive training.

Summary of Progress to Date

A. Drug Effects on Prepulse Inhibition of Startle:

1. We carefully examined the effects of 4 dopamine agonists (amphetamine, 20 mg), bromocriptine, 1.25 mg), pramipexole (0.125 and 0.175 mg) and amantadine, 200 mg) and one NMDA antagonist (memantine, 20 and 30 mg) on prepulse inhibition (PPI) and related measures, and reported on these effects in five papers (below). Paradigms were modified to increase the sensitivity to drug effects (e.g. via use of within-subject designs or optimal stimulus parameters), and new paradigms were developed to provide new insights into these drug effects (e.g. via the development of a novel sensory gating paradigm). Our findings identified quite distinct effects of these drugs in our behavioral paradigms; for example, amphetamine on the one hand, and amantadine and memantine on the other, produced opposite effects on PPI, with amphetamine significantly disrupting and amantadine and memantine significantly increasing PPI. These effects were not predicted based on our preclinical findings in rats, and have led to new hypotheses and insights related to cross-species differences in the regulation of sensorimotor gating.

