1. The "WITHIN-SUBJECT" study involves a single drug. There will be 2 test days – on the additional test day, subjects will receive either placebo or an active dose of one of the following: amphetamine (20 mg), memantine (10 mg) and memantine (20 mg). Some studies may require a venopuncture for genetic analysis as discussed above. A "model" example of a WITHIN-SUBJECT test schedule is shown below:

Test Day 1

0815-0845 Subject signs required forms, provides urine sample, eats standardized breakfast, venopuncture (if required)

0845-0900 Vital signs (VS) check, hearing and vision test, symptom rating scale.

0900-0915 drug or placebo administration.

0915-0930 VS check; symptom rating scales.

0930-0945 EMG electrodes applied.

0945-1000 VS check; symptom rating scales.

1000-1125 Startle response measurement, including PPI, habituation and intensity assessment.

1125-1140 VS check; symptom rating scales.

1140-1155 Visual LI or Visuospatial priming or MCCB

1155-1210 VS check; symptom rating scales.

1210-1300 Subject offered lunch from cafeteria.

1300-1600 VS check hourly; subject dismissed if VS within established parameters at 1600.

Test Day 2: 7-30 days after Test Day 1

0815-0845 Subject signs required forms, provides urine sample, eats standardized breakfast, venopuncture (if required)

0845-0900 Vital signs (VS) check, hearing and vision test, symptom rating scale.

- 0900-0915 drug mg or placebo administration: WHICHEVER DOSE WAS NOT RECEIVED ON TEST DAY 1
- 0915-0930 VS check; symptom rating scales.
- 0930-0945 EMG electrodes applied.
- 0945-1000 VS check; symptom rating scales.
- 1000-1125 Startle response measurement, including PPI, habituation and intensity assessment.
- 1125-1140 VS check; symptom rating scales.
- 1140-1155 Visual LI or Visuospatial priming or MCCB
- 1155-1210 VS check; symptom rating scales.
- 1210-1300 Subject offered lunch from cafeteria.
- 1300-1600 VS check hourly; subject dismissed if VS within established parameters at 1600.

Subjects will be instructed to not eat on the morning of the test, and instead will be served a standardized meal 30 min prior to drug administration, so as to maintain a controlled and consistent impact on drug absorption.

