Main effects of memantine on WM will be tested by one-way ANOVA with memantine dose as a withinfactor. Based on d=0.73 for increased WM after 20 mg MEM in controls (see above), the proposed 30 patients/dose group would yield power of 0.79 to detect significant WM-enhancing effects. While preliminary data yield less robust predictions for COMT subgroup sensitivities in memantine effects on WM performance, given the significant correlation of WM and PPI, and known impact of COMT genotype on PPI levels, we predict some differential (Val/Val > Met/Met) memantine sensitivity in this measure. If we estimate effects of COMT status on WM memantine-sensitivity to be comparable to those for PPI (65% increase in effect size), then the estimated d for Val/Val vs. Met/Met sensitivity should be 1.20, and the proposed genotype subgroup sizes would yield power of 0.65 to detect genotype-sensitive memantine effects on WM.

Secondary "biomarkers" are MMN and GBS. For MMN, positive memantine effects will be detected by increased MMN amplitude at electrode Fz. For GBS, positive memantine effects would be detected by increased 40 Hz evoked power at electrode Fz. Unlike those for PPI, predictions of positive memantine effects on MMN and GBS are not based directly on previous findings from our laboratory, using measures identical to those proposed herein. However, based on reports in healthy subjects from other laboratories of memantine effects on MMN (d=0.87) and ketamine effects on GBS (d=0.69), the proposed 30 patients/dose group would yield power of 0.90 and 0.75, respectively, to detect positive memantine effects on these measures.

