30. PROCEDURES FOR SURROGATE CONSENT AND/OR DECISIONAL CAPACITY ASSESSMENT

Schizphrenia patients who have been identified for participation in our studies will also be enrolled in IRBapproved clinical trials of cognitive training with [name]. [name] has approval to screen and administer surrogate identification process. Any patients that have been identified as having impairment in their decision-making ability will be determined by [name] and will not be referred to our studies.

Revision date: October 29, 2010

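### Minor, cheap improvement: the patient working-memory test has dose as its only factor, although testing is repeated 7-30 days apart and no dose-order balance is stated for patients

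*Protocol*

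**What the plan says.** Section 9.j fixes the patient WM analysis: "Main effects of memantine on WM will be tested by one-way ANOVA with memantine dose as a withinfactor". The same section has each dose group analysed separately, so each test compares placebo with one active dose in 30 patients. It plans power of 0.79 from d=0.73 seen in controls.

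Aim 3 (section 6) has patients "completing measures of sensorimotor gating and neurocognition on each test day". The model schedule in section 9.g lists "1140-1155 Visual LI or Visuospatial priming or MCCB" on both days and sets "Test Day 2: 7-30 days after Test Day 1". The Day 2 dose is "WHICHEVER DOSE WAS NOT RECEIVED ON TEST DAY 1". Nothing says how the Day 1 dose is chosen for patients.

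Order balance is stated only in section 8, for the memantine study in normal subjects: "This ongoing study is conducted with a double- blind, balanced order design".

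The sections differ on what else the patients are doing:
- Section 30: "Schizphrenia patients who have been identified for participation in our studies will also be enrolled in IRBapproved clinical trials of cognitive training".
- Section 8 describes the planned patient work as being in "patients with schizophrenia, who are enrolled in IRB-approved clinical trials of cognitive training".
- Section 15 says the patients will come mainly or only from people seeking to join a supported-employment protocol. It does not mention training.

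The SAP covers PPI, MMN and ASSR. It contains no WM analysis.

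**The concern.** In a two-day crossover, anything that moves scores between Day 1 and Day 2 is separable from drug only if both orders occur and the model or the balance allows for the day. Repeated neurocognitive testing makes such a shift plausible for WM. Cognitive training between the two days could add to it, but the documents give no timing for any training, and section 15 does not match sections 8 and 30.

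A dose-only model handles a shift in one of two ways. With balanced order, the shift goes into the error term and the test becomes conservative. With unequal order, part of the shift also moves the drug estimate. Without a day term or counts per order, a reader of a WM result cannot tell which of these happened or how much it mattered.

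**Working it through.** **Inputs from section 9.j:** d=0.73; 30 patients per dose group; 24 at maximum expected attrition (a figure given for PPI); alpha 0.05, taken as two-sided.

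**Assumptions (not in the documents):** the within-patient correlation r, and the day shift s.

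**The planned figure.** Noncentral t for two independent groups of 30 with d=0.73 gives power 0.794, which matches the stated 0.79. A paired test with r=0 gives 0.780. A paired test with r=0.5 gives 0.971. The stated 0.79 is therefore not evidence that repeated WM scores are uncorrelated, and r has to be varied.

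**Model.** Let D be memantine minus placebo for one patient, scaled so that SD(D)=1.
- Drug on Day 2: mean of D = τ + s.
- Drug on Day 1: mean of D = τ − s.
- τ = 0.73/√(2(1−r)), which is 0.516 (r=0), 0.73 (r=0.5) or 1.154 (r=0.8).

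The planned test is a one-sample t on D. The day-term test is the intercept of D regressed on order (+1/−1), with n−2 df.

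**Effect of s on the planned test.**
- Equal order: the mean of D stays at τ, and its variance becomes about 1 + s² (1.0625 at s=0.25, 1.25 at s=0.5).
- Unequal order: the estimate moves by (difference in order counts / n) × s. At 20:10 that is (20−10)/30 = one third of s. At 14:10 among 24 completers it is 4/24 = one sixth of s.

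**Type I error by simulation, n=30, s = 0.25 / 0.5:**

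| Order split | Dose only | With day term |
|---|---|---|
| 15:15 | 0.043 / 0.029 | 0.05 |
| 18:12 | 0.051 / 0.053 | 0.05 |
| 20:10 | 0.066 / 0.10 | 0.05 |
| Coin-flip, averaged | 0.05 / 0.05 | 0.05 |

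Under coin-flip order, a split of 20:10 or worse occurs in 9.9% of samples of 30.

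**Power by simulation:**

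| n, order | r | Dose only, s = 0 / 0.25 / 0.5 | With day term |
|---|---|---|---|
| 30, 15:15 | 0 | 0.781 / 0.762 / 0.702 | 0.78 |
| 30, 15:15 | 0.5 | 0.972 / 0.967 / 0.951 | 0.972 |
| 30, coin-flip | 0 | 0.781 / 0.755 / 0.686 | 0.765 |
| 30, coin-flip | 0.5 | 0.972 / 0.963 / 0.934 | 0.966 |
| 24, 12:12 | 0 | 0.678 / 0.654 / 0.586 | 0.676 |
| 24, 12:12 | 0.5 | 0.930 / 0.918 / 0.887 | 0.927 |
| 24, coin-flip | 0 | 0.678 / 0.653 / 0.582 | 0.658 |
| 24, coin-flip | 0.5 | 0.929 / 0.913 / 0.865 | 0.915 |

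**Scale of the shift.** If the shifts are 0.25 / 0.5 of the between-person SD (r=0, n=30), power without the term is 0.770 / 0.742 at 15:15, against 0.779 with it. Under coin-flip order it is 0.768 / 0.731 against about 0.765, so the smaller shift brings no gain.

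**High correlation.** The WM figure caption in section 8 gives F=10.68 in 8 subjects, but leaves unclear whether this is the WM test or the PPI test. If it is WM, then dz = √(10.68/8) = 1.155 and r = 1 − (0.73/1.155)²/2 = 0.80. Power is then about 0.99 or more with or without the term. Calibration still differs by split: with shifts of 0.25 / 0.5 between-person SD, dose-only type I error is 0.035 / 0.013 at 15:15 and 0.085 / 0.147 at 20:10, against 0.05 with the term.

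**The case against.** The strongest reply is that very little is at stake. Five parts of it deserve an answer.

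- **Every shift is assumed.** No retest gain is given, the documents do not say whether the same test forms are repeated, and the model schedule offers the MCCB as one of three alternatives. This stands, although Aim 3 does put neurocognition on both days.
- **The power gain is small where r is realistic.** At r=0.5 and s=0.25 with 15:15 order it is about half a percentage point, and at r near 0.8 it is nil. This stands. The visible gains come mainly from r=0, which the stated 0.79 does not establish.
- **Section 9.j allows mixed-design ANOVAs where suitable for other measures.** Such a model could carry an order factor. But no day or order term is named, and the specific WM sentence lists dose alone.
- **The control and patient memantine studies share one schedule and one design label.** Balanced order may well have been used for patients too. That is possible. The gap is one of reporting, and silence does not show imbalance.
- **The training premise is unsettled.** Section 15 describes a different source of patients, and the timing of training is not given. This stands, so the point rests on repeat testing alone, with training as a possible addition.

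A reader might infer that the WM result is biased, or that training is mixed up with the drug effect. The documents support neither: they report no WM result or order counts for patients, and over random order the shift averages to zero.

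**Conclusion.** The point holds as a minor improvement. The planned WM test omits a standard crossover term, and patient order is undocumented. If order was balanced, the omission makes the test conservative. If the realised order was unequal, the estimate moves by the imbalance fraction times the shift, and type I error at that split can depart from 0.05 (0.066 or 0.10 at 20:10 under the assumed shifts). It is not a systematic bias under random order. The power benefit ranges from nil to about 8 percentage points (0.702 against 0.78 at r=0, s=0.5, 15:15), depending on r and s, neither of which the documents supply. At high r, only calibration at the realised split remains.

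It would be tempting to extend this to the SAP's statements that its hypotheses were confirmed. That is not supported: WM is not in the SAP, and no day shift is argued here for PPI, MMN or ASSR.

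**What to change.** - Add test day (1 vs 2) as a fixed effect in the WM main-effect model: either a mixed model with drug, day and random subject, or a two-sequence crossover ANOVA. If WM has already been analysed, report this beside the existing result as a sensitivity analysis.
- State how the Day 1 dose was assigned to patients, and report counts per order in each dose group. The day term works only if both orders occur.
- Reconcile sections 8 and 30 with section 15, and say whether any cognitive training fell between the two test days.

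**Cost.** One degree of freedom; test day is already fixed by the schedule. If there is no day effect, power falls by under 0.3 percentage points at exact balance. Under coin-flip order it falls by 1.5 points (n=30, r=0: 0.781 to 0.766), about 2 points (n=24, r=0), 0.6 points (n=30, r=0.5) or 1.3 points (n=24, r=0.5).

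The term need not go into the 11 vs 7 genotype contrast on WM (d=1.20, stated power 0.65). Simulated power there falls from 0.647 to 0.616 with no shift, is level at s=0.25 (0.616 against 0.612), and gains only at s=0.5 (0.544 against 0.614).
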